#### **6.1.4 End-of-treatment visit in Part A (Week 26)**

On Day 182, patients will undergo the following procedures:

- Serum or urine pregnancy test (if applicable)
- Body weight
- Physical examination (full)
- Vital signs
- SLE panel
- Hematology panel
- Coagulation panel
- Clinical chemistry panel
- Urinalysis
- Solicited symptomatic anemia assessment
- QOL assessment (FACIT-Fatigue, EQ-5D-5L, SF-12, PGIS, and PGIC)
- ADAs against BIVV009 (predose) or at ET if patient withdraws early.
- PK and PD sampling
- Disease-related biomarkers
- Record healthcare resource utilization data since previous assessment
- Record concomitant medications/procedures including transfusions
- Adverse event monitoring

After completion of all Part A EOT assessments, a cross-over loading dose will be administered to patients in a blinded manner at the Week 26 visit to initiate dosing in Part B.

#### **6.1.5 Part B extension phase**

##### **6.1.5.1 Procedures to be performed every 2 weeks**

For patients completing Part A, the following procedures will be performed every 2 weeks (beginning at Week 27) during Part B prior to administration of study drug:

- Hematology panel
- Clinical chemistry panel
- Solicited symptomatic anemia assessment
- Record concomitant medications/procedures including transfusions
- Adverse event monitoring

#### **6.1.5.2 Procedure to be performed every 4 weeks**

- Women of childbearing potential will undergo serum or urine pregnancy testing every 4 weeks (beginning at Week 27) during Part B prior to administration of study drug.
- Record healthcare resource utilization data.

#### **6.1.5.3 Procedures to be performed every 3 months**

In addition, the following procedures will be performed every 3 months beginning after Week 27 (or as otherwise noted) during Part B prior to administration of study drug:

- Body weight
- Physical examination (brief)
- Vital signs
- Urinalysis
- QOL assessments:
  - FACIT-Fatigue
  - EQ-5D-5L
  - SF-12
  - PGIS
  - PGIC
- 12-lead ECG (once at 3 months [Day 273])
- SLE panel (every 6 months)
- PK, PD, and ADA sampling

At 0 hour, study drug will be infused via an indwelling IV catheter over a period of 60±5 minutes. Patients with underlying cardiopulmonary disease may receive a 2-hour infusion with Sponsor approval. Additionally, study drug infusion may be interrupted or slowed in the event of suspicion of an allergic or anaphylactic reaction.

After completion of the infusion, patients will undergo the following procedures:

- Vital signs at 1 hour (±5 minutes) postdose

- 12-lead ECG (once at 3 months [Day 273]) at 1 hour ( $\pm 15$  minutes) postdose
- PK and PD sampling (every 3 months) at 1 hour ( $\pm 15$  minutes) postdose

#### **6.1.5.4 Additional PK, PD, and ADA sampling**

PK and PD samples will continue to be collected at predose and 1 hour (+/- 15 minutes) post-dose on Days 189, 217, and 245.

ADA samples will be collected at predose, on Day 189, 217, and 245.

PK, PD, and ADA samples will be collected if a patient experiences a hematologic breakthrough event (rapid fall in Hgb  $\geq 2$  g/dL associated with an increase in LDH/bilirubin and/or decrease in haptoglobin since the last scheduled visit).

#### **6.1.5.5 Infusion of the study drug at patient's home**

Home infusions will be performed at pre-selected countries/sites by a healthcare professional caregiver contingent upon completion of training delivered by the Investigator or delegated site staff member only in patients willing to be administered study drug at home, who have been treated for at least 3 months (completed visit Day 273) in Part B and in whom previous on-site infusions were uncomplicated (for the US, the Netherlands, Norway, France, Italy, Austria, Germany, and Spain, specific amendments) ([Appendix K](#)). Only patients who do not participate in, or have never participated in undiluted infusions can be considered for home infusion.

#### **6.1.5.6 Infusion of the undiluted study drug**

A subset of patients in Part B will be proposed to receive infusions with study drug undiluted with saline solution. Undiluted infusions may begin no sooner than after Week 39 (Day 273) in patients who consent to and without evidence of intolerance to the study drug and who satisfy criteria outlined in [Section 4.1](#). Only patients who do not participate in, or have never participated in home infusion can be considered for undiluted infusions. Each qualified patient is supposed to receive at least one undiluted infusion of BIVV009, however patients are free to continue with undiluted BIVV009 until the end of study. Post-infusion vital signs will be collected for these patients. Patients receiving undiluted infusions of BIVV009 may return to diluted infusions any time, or this may be the Investigator's decision. Patients receiving undiluted BIVV009 will return to diluted infusions if they experience adverse event that in the opinion of the Investigator, may jeopardize patient safety if undiluted infusions are continued. Patients may return to diluted infusions if this AE is considered by the Investigator to be unrelated to BIVV009 and once resolved or stabilized. Hypersensitivity or allergic reactions to study drug will always result in study drug discontinuation and withdrawal from the study.

#### **6.1.5.7 Early termination/end of study/safety follow-up visit**

Upon completion of dosing in the study, or if a patient terminates the study early, the following assessments should be completed 9 weeks after administration of the last dose of study drug:

- Serum or urine pregnancy test (if applicable)

- Body weight
- Physical examination (full)
- Vital signs
- SLE panel
- Hematology panel
- Coagulation panel
- Clinical chemistry panel
- Urinalysis
- Solicited symptomatic anemia assessment
- QOL assessments (FACIT-Fatigue, EQ-5D-5L, SF-12, PGIS, and PGIC)
- ADAs against BIVV009
- PK and PD sampling
- Record healthcare resource utilization data since previous assessment
- Record concomitant medications/procedures including transfusions
- Adverse event monitoring

If a patient experiences a hematological breakthrough event during the safety follow-up period, a PK, PD, and ADA sample should be collected at the time of the event.

## **6.2 STUDY TREATMENT**

### **6.2.1 Drug supplies and accountability**

Patients will receive doses of either 6.5 grams or 7.5 grams of BIVV009, depending on their body weight. BIVV009 is supplied to the pharmacy for preparation for infusion in either 10 mL glass vials (18 mg/mL) or 25 mL glass vials (50 mg/mL); for subjects receiving undiluted infusions, BIVV009 is supplied in 25 mL glass vials (50 mg/mL). The Sponsor (or designee) will provide the Investigators (or designees) with adequate quantities of BIVV009 and placebo. BIVV009 drug product will be provided as a sterile, nonpyrogenic, isotonic aqueous solution containing 18 mg/mL or 50 mg/mL BIVV009 with 10 mM sodium phosphate buffer, 140 mM NaCl, 0.02% polysorbate 80 (Tween-80), and water for injection; the pH is 6.1. Each Type 1 glass vial, which has a bromobutyl rubber stopper and an aluminum seal, contains sufficient overfill to account for vial, needle, and syringe loss. Drug product can be used for IV administration only.

BIVV009 placebo is manufactured and packaged in the same configuration as the BIVV009 drug product, but without BIVV009. BIVV009 placebo will be provided as a sterile, nonpyrogenic, isotonic aqueous solution containing 10 mM sodium phosphate buffer, 140 mM NaCl, 0.02% polysorbate 80 (Tween-80), and water for injection; the pH is 6.1. Each Type 1 glass vial, which

has a bromobutyl rubber stopper and an aluminum seal, contains sufficient overfill to account for vial, needle, and syringe loss. BIVV009 placebo can be used for IV administration only.

BIVV009 and BIVV009 placebo should be stored at 2°C to 8°C, protected from light, and kept under secure conditions until immediately before use. It is to be administered via IV infusion according to the instructions given in the Pharmacy Manual for this study.

Preparation and accountability procedures for the investigational product including those associated with home infusions (for the US, the Netherlands, Norway, France, Italy, Austria, Germany, and Spain) specific amendments ([Appendix K](#)), whenever applicable, are described in further detail in the Pharmacy Manual.

### **6.2.2 Patient number and identification**

Patients will be assigned unique study numbers that will be used on all study documentation during the course of the trial. For patients who are withdrawn by an Investigator (or designee) or who voluntarily withdraw prematurely from the study, replacement patients will be enrolled only if deemed necessary by the Sponsor. Numbers will not be reused.

### **6.2.3 Randomization**

On Day 0, eligible patients will be randomized in a 1:1 ratio to treatment with either BIVV009 or placebo using an Interactive Web-based System (IWRS). Details on the randomization process are available in the eCRF Completion Guidelines.

### **6.2.4 Dose preparation and administration**

Qualified pharmacy or clinical staff will prepare each unit dose of study drug for IV infusion. Dose preparation shall proceed as detailed in the Pharmacy Manual for this study. Briefly, placebo or an appropriate number of 10 mL drug product glass vials (each containing 180 mg of BIVV009) or 25 mL drug product glass vials (each containing 1.1 grams of BIVV009) will be pooled and diluted with saline solution to a total volume of 500 mL to administer either a 6.5 gram dose (for patients <75 kg) or a 7.5 gram dose (for patients ≥75 kg), depending on the patient's baseline (Day 0) body weight.

For subjects receiving undiluted infusions, appropriate number of 25 mL drug product glass vials (each containing 1.1 grams of BIVV009) will be pooled to administer either a 6.5 gram dose/130 mL (for patients <75 kg) or a 7.5 gram dose/150 mL (for patients ≥75 kg), depending on the patient's baseline (Day 0) body weight. Details are provided in the Pharmacy Manual.

Study drug or placebo will be infused IV by a suitable infusion pump over a period of approximately 60 minutes. (Patients with underlying cardiopulmonary disease may receive a 2-hour infusion with Sponsor approval.) The infusion catheter and tubing will be flushed both immediately before and immediately following completion of the infusion with a sufficient quantity of sterile saline for injection. For each dose, the patient's actual dose, time of dosing, if the administration is being performed at the patient's home ([Appendix K](#)), or if study drug is administered in the form of undiluted infusions will be recorded in the source documents and

transcribed onto the eCRFs. The administration location, rate, start time, stop time, any infusion interruptions, and total volume of investigational product actually administered will be recorded in the eCRFs. If an AE occurs during the administration of study drug, the rest of the infusion during which the AE occurred may be slowed or stopped at the discretion of the Investigator or the professional healthcare caregiver in case of home infusions ([Appendix K](#)).

Patients must be monitored for acute allergic reactions during infusion and for at least 2 hours after the completion of the first administration of study drug or 1 hour after the completion of each administration of study drug thereafter. Additionally, patients undergoing home infusions will be monitored by the professional healthcare caregiver for 2 hours after the completion of the first home infusion or 1 hour after the completion of each subsequent home infusion ([Appendix K](#)). Epinephrine, parenteral diphenhydramine and, for infusions carried at the study site, cardiac resuscitation equipment, must be immediately available in case an allergic reaction or anaphylaxis occurs. Site personnel or professional healthcare caregiver in case of home infusions ([Appendix K](#)), must be qualified to detect allergic reactions and anaphylaxis and treat those reactions under the guidance of the PI. The home infusion personnel will be trained in basic life support (cardiopulmonary resuscitation [CPR]) but will not be required to have equipment to perform advanced life support (eg, defibrillators). See [Section 6.3.8](#) for further details regarding additional testing.

Patients should be instructed to report the development of rash, hives, pruritus, flushing, urticaria, etc, that may represent an allergic or hypersensitivity reaction to study drug. If any signs or symptoms of an allergic or anaphylactic reaction are observed during the infusion, administration of study drug must be immediately discontinued and the patient treated as appropriate. In case of home infusion, the investigator has to be notified immediately to guide treatment ([Appendix K](#)).

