# 1 SYNOPSIS

Title of Study:	Cadenza Study: A Phase 3, Randomized, Double-Blind, Placebo-Controlled Study to Assess the Efficacy and Safety of BIVV009 in Patients with Primary Cold Agglutinin Disease Without a Recent History of Blood Transfusion
Overview of Study Design:	
This is a randomized, double-blind, placebo-controlled, multicenter study in patients with primary cold agglutinin disease (CAgD) without a recent history of blood transfusion. Eligible patients will receive study drug (BIVV009 or placebo) and undergo safety and efficacy assessments for 6 months (26 weeks) during Part A.
 
Following completion of the initial 6-month treatment period (Part A), patients will roll into the open-label long-term safety and durability of response extension phase (Part B) during which they will receive BIVV009.
 
For the purpose of marketing authorization application, an interim analysis of safety and efficacy data will be performed after all patients have completed the double-blind treatment period (Part A). The Part B open-label extension study will run for 1 year following last patient out (LPO) under Part A.

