**Table 2 - Responder definition**

A patient will be considered a responder in Part A if:

- Hgb increases  $\geq 1.5$  g/dL from baseline (defined as the last Hgb value before administration of the first dose of study drug) at treatment assessment endpoint (defined as mean value from Weeks 23, 25, and 26) and
- The patient did not receive a blood transfusion from Week 5 through Week 26 (EOT), and
- The patient did not receive treatment for CAgD beyond what is permitted per protocol from Week 5 through Week 26 (EOT)

A list of excluded concomitant medications, as well as allowed concomitant medications with restrictions, is provided in [Section 6.2.6](#). Beyond the permitted concomitant medications, study drug, and transfusions, patients may receive no other therapies for the treatment of CAgD while enrolled in this study; patients requiring other treatment for their CAgD in Part A will be withdrawn from the study and counted as non-responders. These patients will not be eligible to participate in Part B.

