## Part B

Following completion of dosing in the initial 6-month treatment period, patients will roll into the long-term safety and durability of response extension phase and receive BIVV009 in an open-label manner. Part B will run for 1 year following last patient out (LPO) under Part A. Patients requiring treatment with permitted concomitant medications and/or transfusions will not be discontinued from the study. Patients in Part B will be transfused per the transfusion criteria in [Table 1](#). Patients who receive a transfusion in Part B will not be withdrawn from the study.

Blinding will be maintained when rolling patients into the extension period by providing a crossover dose at Week 26 to allow placebo patients to receive the BIVV009 loading dose at start of BIVV009 dosing. Patients who were randomized to BIVV009 during the 6-month treatment period will receive a placebo dose at Week 26 to maintain blinding. All patients will then continue to receive bi-weekly BIVV009 dosing starting at Week 27.

Patients will be dosed with BIVV009 every 2 weeks, as in Part A. Should patients deviate from their scheduled dosing, a repeat loading dose may be required. On-site visits will be completed ~ every 3 months (at a minimum) for collection of PK, PD and ADA samples, and additional safety and efficacy measures.

Home infusion will be performed by a healthcare professional caregiver contingent upon completion of training delivered by the Investigator or delegated site staff member only in patients willing to be administered study drug in home, who have been treated with at least 3 months with BIVV009 in Part B and who satisfy the criteria mention in the appendix K ([Appendix K](#)).

A subset of patients from countries pre-selected to participate in home infusion, who have been treated for a minimum 3 months (completed visit Day 273) in Part B and who were determined

to have tolerated BIVV009 well, will be invited to have infusions with BIVV009 performed at their homes, after having been qualified by the Investigator. Home infusion will be performed by a healthcare professional caregiver contingent upon completion of training delivered by the Investigator or delegated site staff member. Patients will follow the alternate home infusion scheme, ie, home infusion at the patient's home will be alternating with office visits, so that patients will attend office visit every 4 weeks alternating with home infusions every 4 weeks ( $\pm 2$  days) ([Appendix K](#)).

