### 7.3 EFFICACY - PART A

#### 7.3.1 Analysis populations

**Full Analysis Set Population:** The Intent-to-Treat (ITT) Population consists of all randomized subjects who received at least 1 dose (including partial dose) of study drug. All subjects in the ITT population will be included in the Full Analysis Set (FAS). For analysis, FAS and the ITT Population are considered exchangeable, but the term FAS will be used in subsequent sections.

**Per-Protocol (PP) Population:** The PP Population is defined as a subset of FAS who do not have any important protocol deviations impacting their efficacy assessments.

The FAS analyses will be the primary analyses and the PP analyses will be considered as supportive.

The patients in the FAS that are excluded from the PP Population will be listed, together with the reason for exclusion from the PP Population.

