5.4 APPENDIX 4 DATA HANDLING CONVENTIONS

Study Day

Study Day is defined as days relative to the date of first dose of study drug (BIVV009 or placebo) in Part A (Day 0 as in the protocol). The Study Day of an event is calculated as

- (date of event – date of first dose of study drug in Part A + 1), if the event is on or after the first dose date;
- (date of event – date of first dose of study drug in Part A), if the event is prior to the first dose date.

The date of the first dose of study drug in Part A is Study Day 1.

Baseline

Baseline measures are defined as the last value prior to the first dose of study drug. If a subject receives a transfusion during the screening period, the baseline measure must be at least 7 days after the transfusion.

Visit Windows

Analysis by study visit will utilize the data recorded on the corresponding nominal visit from electronic Case Report Forms (eCRFs). In case of missing data/assessments for a visit, data from an unscheduled visit, or ET/Safety Follow-up Visit will be used, if the Study Day of such a visit fits in the analytic window defined in [Table 14](#), below. If multiple values are identified within the analytic window, the one closest to the target study day will be used.

[figure not shown]
Table 14 - Analyses window definition

[figure not shown]
Visit	Target Study Day	Analytic Visit Window
Baseline (Day 0)	1	≤1
Week 1 (Day 7)	8	2 – 15
Week 3 (Day 21)	22	16 – 29
Week 5 (Day 35)	36	30 – 43
Week 7 (Day 49)	50	44 – 57
Week 9 (Day 63)	64	58 – 71
Week 11 (Day 77)	78	72 – 85
Week 13 (Day 91)	92	86 – 99
Week 15 (Day 105)	106	100 – 113
Week 17 (Day 119)	120	114 – 127
Week 19 (Day 133)	134	128 – 141
Week 21 (Day 147)	148	142 – 155
Week 23 (Day 161)	162	156 – 169
Week 26 (Day 175)	176	170 – 179
Week 26 (Day 182; EOT Visit in Part A)	183	180 – 189

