1 INTRODUCTION

1.1 STUDY DESIGN

BIVV009-04 is a Phase 3, randomized, double-blinded, placebo-controlled, multicenter study in patients with primary cold agglutinin disease (CAD) without a recent history of blood transfusion. Eligible patients received study drug (BIVV009 or placebo) and underwent safety and efficacy assessments for 6 months (26 weeks) in Part A of the study.

Following completion of the initial 6-month treatment period, patients will roll into the long-term safety study (Part B) where they will continue to receive the study drug, BIVV009. After completion of all Part A EOT assessments, patients who qualify to roll-over into Part B will receive a cross-over loading dose, in a blinded manner, at the Week 26 visit. Patients who were randomized to placebo during the 6-month treatment period will receive BIVV009; and patients who were randomized to BIVV009 during the 6-month treatment period will receive a placebo dose in order to maintain the blinding. Part B will run for one year following last patient out (LPO) under Part A. In Part B, patients will be dosed with open-label BIVV009 every two weeks, as in Part A. On-site visits will be completed every two weeks when samples for safety and efficacy measures will be collected; samples for pharmacokinetics (PK) and pharmacodynamics (PD) will be collected at visits approximately every three months. Sample for antidrug antibodies will be collected every three months (at a minimum). The study will be complete 12 months following LPO under Part A at which time all patients receiving on-going treatment will proceed to an End-of-Study (EOS) visit 9 weeks after the last administration of study drug.

After Week 39, a subgroup of patients will have their study drug infused at home, every four weeks, alternating with study drug administration during office visits. Additionally, after Week 39, another subgroup of patients will have their study drug administered in the form of infusions undiluted with normal saline.

Study primary analysis will be conducted for Part B after all patients have completed Part B and the data are cleaned.

This statistical analysis plan contains information pertaining to definitions of analysis sets and derived variables, and statistical methods for the analysis of efficacy, safety, PK, and PD for Part B of the referenced study.

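### Placebo patients' first BIVV009 infusion, at the blinded Week 26 crossover, carries only the 1-hour allergic-reaction observation, because the 2-hour period is tied to Day 0 in both arms

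*Protocol*

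**What the plan says.** Protocol section 6.2.4 sets the rule for infusions at the site. Patients are watched for acute allergic reactions during the infusion and then "for at least 2 hours after the completion of the first administration of study drug or 1 hour after the completion of each administration" that follows. For home treatment, the same section starts a new 2-hour period at the first home infusion.

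The documents use study drug for whichever product the patient is randomised to. The synopsis reads "Eligible patients will receive study drug (BIVV009 or placebo"), and the Part A SAP (section 5.4) counts study days from the "date of first dose of study drug (BIVV009 or placebo) in Part A", which it equates with Day 0. Section 6.1.2 labels the Day 0 visit as the first dose.

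For Part B, section 4.1 provides a Week 26 crossover dose "to allow placebo patients to receive the BIVV009 loading dose at start of BIVV009 dosing". The Part B SAP (section 1.1) describes the same dose: "Patients who were randomized to placebo during the 6-month treatment period will receive BIVV009", while the BIVV009 arm gets placebo. Section 6.1.4 states: "After completion of all Part A EOT assessments, a cross-over loading dose will be administered to patients in a blinded manner".

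**The concern.** A longer watch at the first dose makes most sense as protection at first contact with the antibody. In the BIVV009 arm it does that. In the placebo arm it is used on Day 0, after a placebo infusion. When these patients meet BIVV009 for the first time at Week 26, the text treats that infusion as just another later dose with a 1-hour minimum.

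The stake is patient safety at a single visit. Judged by the protocol's own standard, one arm gets less protection at first active exposure than the other. No efficacy result depends on it.

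**Working it through.** No figure in the plan needs reproducing. The check maps the observation rule onto each arm's dosing sequence and then looks for any other rule that covers Week 26.

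**1. Which dose is the first administration of study drug?** The synopsis and Part A SAP section 5.4 include placebo in the term, and section 6.1.2 places the first dose on Day 0. Section 6.1.1 defines screen failures as consented patients never dosed with either product. Two efficacy definitions show the same usage: baseline Hgb is "defined as the last Hgb value before administration of the first dose of study drug" (Table 2), and the analysis set is "all randomized subjects who received at least 1 dose (including partial dose) of study drug" (section 7.3.1). Both must work in the placebo arm, so the first dose there is the Day 0 placebo infusion.

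**2. Dosing sequence.** Part A has 14 infusions: Day 0, Day 7, then every 14 days from Day 21 to Day 175. The Week 26 crossover (Day 182) is number 14 + 1 = 15 if none is missed.

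| Infusion | BIVV009 arm | Placebo arm | Minimum observation |
|---|---|---|---|
| Day 0 | BIVV009 (first exposure) | placebo | 2 h |
| Days 7 to 175 (13 doses) | BIVV009 | placebo | 1 h each |
| Day 182, crossover | placebo | BIVV009 (first exposure) | 1 h |
| Week 27 onward, on site | BIVV009 | BIVV009 | 1 h each |

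Shortfall at first active exposure in the placebo arm: 2 h − 1 h = 1 h.

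**3. Does anything else cover Week 26?**
- Section 6.1.4 gives no observation time and lists no post-infusion procedures for the crossover dose. Sections 6.1.2, 6.1.3 and 6.1.5.3 do list them for their visits.
- Table 3, footnote g, adds vital signs 1 hour after each dose, which does not extend the watch.
- The only restart of the 2-hour period is at the first home infusion. Those patients have had at least 3 months in Part B without hypersensitivity (Appendix K), so they already tolerate the drug.

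**4. How many patients?** Section 7.10 plans 40 patients, 20 per group.
- Upper bound: 20 placebo patients.
- Some will not cross over, for example those who withdraw after Week 5 and before Week 23 (section 5.3). The documents give no rate. With an assumed 0% to 20%: 20 × 1.00 = 20 down to 20 × 0.80 = 16.

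**5. How many could still benefit?** Part B enrolment began on 27-Nov-2018 (Part B SAP, version history), and protocol Version 8 is dated 04 November 2020. The interval is 731 − 23 = 708 days, about 23 months. The documents do not say how many crossovers remained, so the range is 0 to 20 in the placebo arm.

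**The case against.** The strongest objection is that study drug in the observation rule could mean BIVV009 alone. Sections 6.2.4 and 6.2.5 each name study drug and placebo as alternatives at one point, and the Part B SAP (section 1.1) calls BIVV009 the study drug. On that reading the 2 hours already fall at Week 26 for placebo patients. The inconsistency is real and needs clearing up. But the narrow reading conflicts with the synopsis and Part A SAP section 5.4, and it leaves placebo infusions with no observation rule. Staff are blinded (section 6.2.5), so they could follow it only by watching everyone for 2 hours at Week 26, which the protocol nowhere says. Either reading needs the same clarification.

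Other points stand in part:
- Table 2 and section 7.3.1 define efficacy terms. They illustrate usage but do not govern a safety rule.
- Placebo has the same buffer and polysorbate 80 (section 6.2.1), so Day 0 did cover first exposure to the excipients. Only the antibody is new at Week 26.
- The Week 26 dose is given on site, with trained staff and with epinephrine, diphenhydramine and resuscitation equipment to hand. One hour is a minimum that a site may exceed. AEs within 24 hours of a site infusion are captured (Part B SAP section 4.7.2).
- The documents hold no data on reaction timing, so the value of the second hour rests only on the protocol's own rule.
- The Pharmacy Manual is not available and might say more.
- The change may come too late. The first patient was randomised on 16 Apr 2018, and the Part B SAP of 20-Jul-2020 describes Part A in the past tense. That does not show that all crossovers were done.

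**Conclusion.** The concern holds and is minor. As written, the 2-hour observation does not fall on the placebo arm's first BIVV009 infusion. At most 20 of 40 patients have a 1-hour instead of a 2-hour minimum there, or 16 to 20 under the assumed 0% to 20% non-entry to Part B. The conclusion rests on study drug including placebo in section 6.2.4, and on no longer period being set in the Pharmacy Manual. The absolute risk cannot be estimated from the documents, and existing safeguards at the visit limit it. The Part A primary analysis is unaffected.

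**What to change.** Amend section 6.2.4 to require at least 2 hours of observation after the Week 26 crossover infusion, as well as after Day 0, for all patients in both arms. Applying it to both arms keeps the blind. Add a cross-reference in section 6.1.4, and use study drug consistently for BIVV009 or placebo in sections 6.2.4 and 6.2.5. The sponsor should first count the crossovers still to come, since the change applies only to those.

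The cost is one extra hour, once per patient, at an existing visit: 1 h × 40 = 40 patient-hours at most, or 1 h × 32 = 32 if 20% of both arms do not enter Part B (an assumption). Half of that time follows a placebo dose and serves only to keep the blind.
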